2.5.3 Handling of missing values/censoring/discontinuations

PFS will be censored if no PFS event is observed before the cut-off date or before the start date of a new anticancer therapy or another investigational treatment, whichever occurs earlier.

The censoring date will be the date of last adequate tumor assessment before either of these two dates. If a PFS event is documented after two or more missing assessments or nonadequate tumor assessments, then the date of PFS will be censored at the date of the last adequate tumor assessment. If a PFS event is observed after a single missing or non-adequate tumor assessment, the actual date of event will be used.

2.5.4 Sensitivity and other supportive analyses

No sensitivity analysis will be performed for final CSR.

2.6 Analysis of the key secondary objective

Not applicable. There is no key secondary endpoint in this study.

2.7 Analysis of secondary efficacy objective(s)

The secondary efficacy objectives in this study are the two treatment groups with respect to OS, ORR, deterioration in the ECOG PS, and CBR.

Additionally, ORR, deterioration in the ECOG PS, CBR, time to response and duration of response will be summarized between the treatment groups in the final CSR. The analysis results for the other secondary efficacy endpoints were provided in the primary CSR [Study Y2202-Section 11]. The analysis of all secondary efficacy endpoints (mentioned below) will be performed on the FAS.

Overall survival (OS)

Overall survival (OS) is defined as the time from the date of randomization to the date of death due to any cause. If the subject is alive at the date of the analysis cut-off or lost to follow-up, then OS will be censored at the last contact date prior to data cutoff date. Only one OS analysis will be performed at the end of the study. The OS analysis will be based on data from the FAS on the ITT basis, i.e., according to the treatment group subjects are randomized to at baseline.

Overall response rate (ORR)

Overall response rate (ORR) is defined as the proportion of subjects with best overall response of complete response (CR) or partial response (PR) according to RECIST 1.1 (Appendix 1 of the protocol). ORR will be calculated based on the FAS according to the ITT principle, using local radiologist's/investigator's tumor assessment. Subjects with bone lesions only at baseline will be included in the numerator if they achieve a complete response.

Clinical benefit rate (CBR)

Clinical benefit rate (CBR) is defined as the proportion of subjects with best overall response of CR, PR, or overall lesion response of stable disease (SD for measurable disease and non-CR/non-PD (NCRNPD) for non-measurable disease) with duration of 24 weeks or longer. A subject will be considered to have a SD/NCRNPD for 24 weeks or longer if SD/NCRNPD is recorded at 24 weeks or later after randomization. Taking into account the allowed time window for tumor assessment visits, the SD/NCRNPD response has to be recorded at 23 weeks or later after randomization to be included in the CBR calculation. Best overall response of CR, PR and overall lesion response of SD/NCRNPD are defined according to RECIST 1.1 (see Appendix 1). CBR will be calculated based on the FAS according to the ITT principle, using local radiologist's/investigator's tumor assessment. Subjects with non-measurable disease only at baseline will be included in the numerator if they achieve a complete response.

Time to response (TTR)

Time to overall response (TTR) of CR or PR is defined as the time from randomization to first documented response (CR or PR, which must be confirmed subsequently) for subjects with a confirmed CR or PR. It will be summarized using local radiologist's/investigator's tumor assessment.

Duration of Response (DOR)

Among subjects with a confirmed response (PR or CR) per RECIST 1.1 by investigator, DOR is defined as the time from first documented response (PR or CR) to the date of first documented disease progression or death due to any cause. It will be summarized using local radiologist's/investigator's tumor assessment.

ECOG performance status

ECOG performance status (PS) scale will be used to assess physical health of subjects, ranging from 0 (most active) to 5 (least active) given in [Table 2.2](#).

ECOG PS will be evaluated at the following visits:

- Baseline (\leq 7 days prior to administration of the study drugs)
- Cycle 1 Day 1 (prior to administration of the study drugs)
- Every 2 Cycles after Cycle 1 Day 1(Cycle 3 Day 1, Cycle 5 Day 1 and etc)
- End of treatment

Table 2-2 ECOG Performance Status Scale

Score	Description
0	Fully active, able to carry on all pre-disease performance without restriction
1	Restricted in physically strenuous activity but ambulatory and able to carry out work of a light or sedentary nature, e.g., light house work, office work
2	Ambulatory and capable of all self-care but unable to carry out any work activities. Up and about more than 50% of waking hours
3	Capable of only limited self-care, confined to bed or chair more than 50% of waking hours
4	Completely disabled. Cannot carry on any self-care. Totally confined to bed or chair
5	Dead

ECOG performance status will be assessed and recorded at baseline, and every two cycles thereafter as well as at discontinuation from the study treatment (within one week after discontinuation).

2.7.1 Secondary endpoints

Overall survival (OS), Objective Response Rate (ORR), Clinical Benefit Rate (CBR), Time to overall response (TTR) and Duration of Response (DOR), Time to deterioration of ECOG Performance Status.

Baseline	On or before Study Day 1	<= Study Day 1
Cycle 1 Day 1	Study Day 1	Study Days 1-8
Cycle 3 Day 1	Study Day 57	Study Days 50-64
Cycle 5 Day 1	Study Day 113	Study Days 106-120
Every 2 Cycles thereafter, Cycle X Day 1; X>1	Study Day $((X-1)*4)*7+1$	Study Days $((X-1)*4)*7-6$ to $((X-1)*4)*7+8$ Note: EOT data visit are included if obtained within 7 days of last non-0 dose intake.

Study Day 1 = randomization date

Frequencies of subjects with ECOG PS values of 0, 1 or ≥ 2 will be used to summarize the ECOG PS data at each time window.

An analysis of the time to definitive deterioration of the ECOG PS by at least one category of the score from baseline will be performed. A deterioration will be considered definitive if no improvements in the ECOG PS are observed at subsequent measurement times during the treatment period following the time point at which the deterioration is observed. (Example 1: if the score is 1 at baseline and then 1, 2, 1, 2, 3 at study days 28, 57, 83, 115, 150, respectively, then the time to definitive worsening is 115 days. Example 2: if the score is 1 at baseline and then 1, 1, 2 at study days 28, 57, 83, respectively, with no assessment of the ECOG performance status after day 83, then the time to definitive worsening is 83 days.)

Death will be considered as worsening of the ECOG PS if it occurs close to the last available assessment where “close” is defined as being within twice the planned period between two assessments. Subjects who die after more than twice the planned period between two assessments will be censored at the date of their last assessment before the cut-off. This avoids overestimating the time to definitive worsening in subjects dying after an irregular assessment scheme. For example, if the last assessment is at week 6 and the subject dies at week 16, the definitive deterioration date will be week 16. On the other hand, if the last assessment is at week 6 and the subject dies at week 22, which is after more than twice the planned period between two assessments (6 weeks) since the last assessment (at week 6), then the subject is censored for definitive deterioration and the censoring date will be week 6. Subjects receiving any further anti-neoplastic therapy prior to definitive worsening will be censored at their date of last assessment prior to the start of therapy. Subjects that have not worsened at the data cut-off point will be censored at the date of last assessment prior to the cutoff.

The Kaplan-Meier estimation method will be used to assess the distribution of time to definitive worsening in the ECOG PS score, stratified by treatment. The estimated treatment-specific median times to definitive worsening will be presented along with 90% confidence intervals. The stratified Cox regression model will be used to estimate the hazard ratio of a definitive worsening in the ECOG PS score, along with the associated 90% confidence interval, comparing the everolimus + exemestane combination therapy with placebo + everolimus therapy.

2.7.3 Handling of missing values/censoring/discontinuations

The same statistical principles will be applied, and supportive analyses conducted as described in [Section 2.5.3](#) for the handling of missing values/censoring/discontinuations.

The partial missing death date will be imputed following the rules in Section 5.4.4, but the complete missing death date won't be imputed. For the purpose of analysis, the patient with a complete missing death date will be censored at the last contact date.

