##### **10.5.1.2 Overall survival**

Overall survival is defined as the time from date of randomization to date of death due to any cause. If the patient is alive at the date of the analysis cut-off or lost to follow-up, then OS will be censored at the last contact date prior to data cutoff date. The analyses for OS will be based on the data from FAS on an ITT basis, according to the treatment group patients are randomized to at baseline. The distribution function of OS will be estimated using the Kaplan-Meier method. The median OS along with 90% confidence intervals will be presented by two treatment groups, along with proportion of patients alive at 3, 6, 9, 12 and 18 months and the associated 90% confidence intervals. The stratified Cox regression will be used to estimate the HR of OS, along with 90% confidence interval.

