##### 14.1.3.2.2 Overall survival

All patients should be followed until death or until patient has had adequate follow-up time as specified in the protocol whichever comes first. The follow-up data should contain the date the patient was last seen alive / last known date patient alive, the date of death and the reason of death (“Study indication” or “Other”).

**Overall survival (OS)** is defined as the time from date of randomization/start of treatment to date of death due to any cause. If a patient is not known to have died, survival will be censored at the date of last known date patient alive.

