2.1.9 Last contact date

The last contact date will be derived for subjects not known to have died at the final analysis cut-off using the sources presented in [Table 2-1](#) below:

Table 2-1 Last contact date data sources

Source data	Condition
Last contact date/last date subject was known to be alive from survival follow-up page	Subject status is reported to be alive. Do not use if subject status is reported unknown.
Start/End dates from further antineoplastic therapy	Non-missing medication/procedure term.
Start/End dates from drug administration record	Non-missing dose. Doses of 0 are allowed.
End of treatment date from end of treatment page	No condition.
Tumor (RECIST) assessment date	Evaluation is marked as ‘done’.
Laboratory collection dates	Sample collection marked as done.
Vital signs date	At least one non-missing parameter value.
Performance status date	Non-missing performance status.
Start/End dates of AE	Non-missing verbatim term.

The last contact date on or before the data cut-off date should be used; the cut-off date should not be used as the censoring date (even in presence of post cut-off data) unless the subject was seen or contacted on the cut-off date.

Imputed dates (e.g., analysis cut-off date programmatically imputed to replace the missing end date of a dose administration record) will not be used to derive the last contact date. Partially imputed dates (i.e., only day or day and month imputed) are allowed to be used for last contact date only if coming from Survival Follow-up page.

The last contact date will be used for censoring of subjects in the analysis of overall survival.

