2.9 Interim analysis

Not applicable.

3 Sample size calculation

Refer to CRAD001Y2202 SAP Addendum 1 for details.

4 Change to protocol specified analyses

No change from protocol specified analysis was made.

5 Appendix

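### SAP 2.7.3 censors a recorded death with no date at last contact, which removes a known OS event and does not fit the plan's own OS censoring conditions

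*SAP*

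**What the plan says.** SAP 2.7.3 treats two kinds of incomplete death date differently. Partial dates go to the imputation rules in SAP 5.4.4. For the other kind, "the complete missing death date won't be imputed", and "the patient with a complete missing death date will be censored at the last contact date".

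The rest of the plan describes OS censoring as follows.

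- SAP 2.7 defines OS as "the time from the date of randomization to the date of death due to any cause" and states: "If the subject is alive at the date of the analysis cut-off or lost to follow-up, then OS will be censored". The censoring time there is the date of last contact. Protocol 10.5.1.2 sets the same two conditions.
- Protocol Appendix 1, section 14.1.3.2.2: "If a patient is not known to have died, survival will be censored at the date of last known date patient alive".
- Protocol Appendix 1, section 14.1.4.5.6, lists two possible censoring reasons for survival: alive, and lost to follow-up.
- SAP 2.1.9: "The last contact date will be derived for subjects not known to have died at the final analysis cut-off".
- SAP 5.4.4 imputes a death date when only the year is known: the end-of-treatment date if the years agree, or 1 January if the death year is later.
- SAP 2.8.2 summarises all deaths and on-treatment deaths separately from the OS analysis.

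**The concern.** A death date can be missing only for someone recorded as having died. The rule therefore takes a patient whose death is known and analyses her as having no event.

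Censoring is harmless when the reason for it is unrelated to the risk of death. Here the reason is the death itself, so the censoring is informative by construction. Kaplan-Meier estimates of OS tend to be too high. If undated deaths are more common in one arm, the OS hazard ratio shifts in that arm's favour. The OS event count could also fall below the number of deaths in the safety summaries of the same report.

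**Working it through.** **1. The plan's own figures.** The plan gives no OS event count, OS precision or number of undated deaths. Its only sizing figure is for PFS (protocol 10.6): at a hazard ratio of 0.62 and 110 events, exp(ln 0.62 ± 1.645 × 2/√110) = 0.453 to 0.848, which matches the stated (0.45, 0.85). That figure does not use this rule.

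**2. The texts side by side.** Take a patient recorded as dead, date wholly unknown.

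| Provision | Does it cover her? |
|---|---|
| SAP 2.7 and protocol 10.5.1.2: censor if alive or lost to follow-up | No: she is not alive, and her status is known |
| Protocol 14.1.3.2.2: censor if death is not known | No: death is known |
| Protocol 14.1.4.5.6: reason is alive or lost to follow-up | Neither describes her |
| SAP 2.1.9: derive last contact if not known to be dead | No: the date that 2.7.3 needs is not derived for her |
| Protocol 14.1.4.5.3 and SAP 5.4.4: incomplete death dates | No: both need at least part of the date |

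Uncertainty about the date does not explain the difference in treatment. Under SAP 5.4.4 a death with only a year later than end of treatment is an event on 1 January, which can be wrong by almost 12 months. With survival contact at least every 3 months (protocol 7.1.6.3), a wholly undated death may be bounded more tightly, between the last contact alive and the report of death.

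**3. Illustration of size, under assumptions.**

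- 160 patients, 1:1, uniform accrual over 18 months (protocol 10.6).
- Exponential OS with medians of 30.98 and 26.55 months, from the earlier phase III trial quoted in protocol 1.1.2. The implied hazard ratio is 26.55/30.98 = 0.857.
- Cut-off about 55 months after the first patient: July 2017 (expected start, Amendment 1) to February 2022 (approval, SAP section 1) is 4 × 12 + 7 = 55. This assumes that approval ended the study.
- Last contact 0 to 3 months before death. The undated share is varied from 0% to 10% of deaths.

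Expected deaths per arm are 80 × [1 − (e^(−37λ) − e^(−55λ))/(18λ)] with λ = ln 2/median. This gives 51.2 (everolimus) and 55.7 (placebo), about 107 in all.

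The table shows averages over 400 simulated trials per row with an unstratified Cox model. The arrow runs from all deaths counted at their true dates to undated deaths censored at last contact.

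| Undated share, everolimus / placebo | Mean undated deaths | Hazard ratio | Median, everolimus | Median, placebo |
|---|---|---|---|---|
| 3% / 3% | 3.3 | 0.863 → 0.860 | 31.6 → 32.3 | 27.3 → 27.7 |
| 5% / 5% | 5.3 | 0.855 → 0.855 | 31.7 → 32.7 | 27.2 → 28.1 |
| 10% / 10% | 10.6 | 0.852 → 0.848 | 31.7 → 34.5 | 27.1 → 29.5 |
| 5% / 0% | 2.5 | 0.867 → 0.826 | 31.9 → 33.0 | 27.6 → 27.6 |
| 0% / 5% | 2.9 | 0.861 → 0.907 | 31.5 → 31.5 | 27.2 → 28.2 |
| 10% / 0% | 5.0 | 0.853 → 0.773 | 31.5 → 34.2 | 27.2 → 27.2 |

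Each row uses its own random draws, so compare within rows. With no undated deaths the two analyses coincide. Counting the same deaths as events at the midpoint of the contact window (ending no later than the cut-off) returned the true-date hazard ratio to within 0.001 and the medians to within 0.1 month.

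**4. Precision.** Losing m of D deaths widens the interval for the log hazard ratio by √(D/(D − m)). For 1 of 120 deaths this is 1.004, for 5 of 100 it is 1.026, and for 10 of 60 it is 1.095.

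**The case against.** The strongest reply is that OS needs a date of death, and without one no time can be computed. The protocol is silent on a wholly missing death date, and SAP 2.7.3 fills the gap openly. Neither OS definition says that its censoring conditions are exhaustive. This stands in part. A reader might infer that the SAP section 4 statement, "No change from protocol specified analysis was made", is false, but the protocol has no explicit rule for this case that the SAP could have changed. The silence does not make the choice a good fit, however: every censoring condition and reason that the protocol does give excludes a patient known to be dead.

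The mismatch with SAP 2.1.9 is partly a drafting gap. The sources in Table 2-1 exist for any patient, so a date could be programmed.

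The case should be rare. A year alone is enough for imputation, complete dates are required (protocol 14.1.4.5.3), missing values are queried (protocol 9.4), and a Death form is collected (protocol 8.1.1). The larger hazard ratio shifts above arise only when all undated deaths fall in one arm. All of this stands.

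Two stronger readings are not supported. A reader might infer that PFS is affected too. SAP 2.7.3 covers secondary endpoints. PFS has its own rules in SAP 2.5.2 and 2.5.3, which censor at the last adequate tumour assessment, and the cross-reference in 2.7.3 carries the PFS principles to the secondary endpoints, not the reverse. A reader might also infer that the patient is credited with continued survival. She leaves the risk set at last contact and adds no time after it. What is lost is the event.

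Finally, any replacement date is a convention. The day after last known alive is the earliest possible date and biases survival time downward, and an undated death first reported after the cut-off may not belong before it. Both points shape the fix.

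**Conclusion.** The rule is wrong as written for OS. It turns a recorded death into a non-event, fits none of the plan's own censoring conditions, and treats a wholly undated death less reasonably than one with only the year known.

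The expected effect is small. The number of undated deaths is not given and may be zero. If 1% to 2% of about 107 deaths were undated (an assumption), that is 1 to 2 patients, and losing 2 widens the log hazard ratio interval by √(107/105) = 1.009. With 3% in both arms, the illustrated medians rise by 0.4 to 0.7 months and the hazard ratio hardly moves. An imbalance between arms matters more, in either direction. OS is a secondary endpoint in an estimation-only study, so no test or power is affected.

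**What to change.** In SAP 2.7.3, count a death known to have occurred by the cut-off but without any date as an OS event. Date it by a prespecified rule between the last date known alive and the earlier of the date the death was reported and the cut-off. The midpoint or the day after last known alive would serve. Keep the present censoring rule as a sensitivity analysis. Extend SAP 2.1.9 so that last contact is also derived for these patients. Report the number of undated deaths by arm.

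The cost is a few SAP sentences, with no new data collection. The imputed date is approximate. The earliest-date convention understates survival time, by at most about 3 months per affected patient if the contact schedule was kept, and by more if contact had lapsed.

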2.8 Safety analyses

For all safety analyses, the safety set will be used. The assessment of safety will be based on the frequency of adverse events and on the number of laboratory values that fall outside of pre-determined ranges.

The overall observation period will be divided into three mutually exclusive segments:

- pre-treatment period: from day of subject's informed consent to the day before first dose of study treatment
- on-treatment period: from day of first dose of study medication to 30 days after last dose of study treatment
- post-treatment period: starting on day 31 after last dose of study treatment.

Safety summary tables will only include on-treatment events/assessments, i.e., those collected no later than 30 days after the date of the last study treatment administration. All safety events/assessments will be listed and those collected in the pre- and post-treatment period will be flagged.

2.8.1 Adverse events (AEs)

2.8.1.1 Coding of AEs

Adverse events are coded using the Medical Dictionary for Regulatory Activities (MedDRA) terminology Version 25.0.

2.8.1.2 Grading of AEs

AEs will be graded according to the Common Terminology Criteria for Adverse Events (CTCAE) version 4.03.

The CTCAE represents a comprehensive grading system for reporting the acute and late effects of cancer treatments. CTCAE v4.03 grading is by definition a 5-point scale generally corresponding to mild, moderate, severe, life threatening, and death. This grading system inherently places a value on the importance of an event, although there is not necessarily proportionality among grades (a grade 2 AE is not necessarily twice as severe as a grade 1 AE).

If CTCAE grading is not available for an adverse event, the severity of mild, moderate, severe, and life-threatening, death related to the AE corresponding to Grades 1 - 5, respectively, will be used. Information about any deaths (related to an Adverse Event or not) will also be collected through a Death form and “End of Post Treatment Disposition eCRF page”.

2.8.1.3 General rules for AE Reporting

AE summaries will include all AEs starting on or after study day 1 (i.e., on or after the day of the first intake of study treatment) and starting no later than 30 days after the last treatment/exposure date. All AEs, deaths and serious adverse events will be listed. AEs starting prior to study day 1 and AEs starting later than 30 days after the last treatment/exposure date will be flagged in the listings.

AEs will be summarized by presenting the number and percentage of subjects having at least one AE and having at least one AE in each body system/primary system organ class, and for each preferred term using MedDRA coding. A subject with multiple occurrences of an AE will be counted only once in the AE category.

Separate AE summaries will be presented by primary system organ class, preferred term, and maximum CTC grade. A subject with multiple CTC grades for an AE will be summarized under the maximum CTC grade recorded for the event. In the summaries presented by grade, all AEs will be pooled regardless of whether they are CTC gradable or not, i.e., regardless of whether the question “CTC AE” on the Adverse Events eCRF is answered ‘Yes’ or ‘No’.

The frequency of CTC grade 3 and 4 AEs will be summarized separately as well as summaries of all deaths and on-treatment deaths.

Any information collected (e.g., CTC grades, relatedness to study drug, action taken, etc.) will be listed as appropriate.

